#### 7.4 Reporting of Unanticipated Problems and Adverse Events to COH DSMC and IRB

**Unanticipated Problems** - Most unanticipated problems must be reported to the COH DSMC and IRB **within 5 calendar days** according to definitions and guidelines at [http://www.coh.org/policy/Policies%20and%20Procedures/REVIEWING\\_AND\\_REPORTING\\_UNANTICIPATED\\_PROBLEMS.pdf](http://www.coh.org/policy/Policies%20and%20Procedures/REVIEWING_AND_REPORTING_UNANTICIPATED_PROBLEMS.pdf). Any unanticipated problem that occurs during the study conduct will be reported to the DSMC and IRB by submitting electronically in iRIS (<http://iris.coh.org>).

**Serious Adverse Events** - All SAEs occurring during this study, whether observed by the physician, nurse, or reported by the patient, will be reported according to definitions and guidelines at [http://www.coh.org/policy/Policies%20and%20Procedures/REVIEWING\\_AND\\_REPORTING\\_UNANTICIPATED\\_PROBLEMS.pdf](http://www.coh.org/policy/Policies%20and%20Procedures/REVIEWING_AND_REPORTING_UNANTICIPATED_PROBLEMS.pdf) and Table 2 below. Those SAEs that require expedited reporting will be submitted electronically in iRIS (<http://iris.coh.org>).

**Adverse Events** - Adverse events will be monitored by the PMT. Adverse events that do not meet the criteria of serious OR are not unanticipated problems will be reported only in the protocol continuation reports and PMT report (see Table 2 below).

**Table 7.3.1 City of Hope Adverse Event and Unanticipated Problem Reporting Timelines for the DSMC and IRB**

**DSMC Risk Level 3 and Risk Level 4 Protocol Reporting Timelines**

Required Reporting Timeframe to the DSMC		
Attribution	Unexpected	Expected
Death while on active treatment or within 30 days of last day of treatment		

Required Reporting Timeframe to the DSMC		
Attribution	Unexpected	Expected
Possibly, Probably, Definitely	5 calendar days	
Unlikely, Unrelated		
Death after 30 days of last active treatment/therapy		
Possibly, Probably, Definitely	5 calendar days	No reporting required
Unlikely, Unrelated	No reporting required	No reporting required
Within 30 days of last active treatment/therapy		
Grades 3 and 4 AND meeting the definition of "serious"		
Possibly, Probably, Definitely	5 calendar days	10 calendar days
Unlikely, Unrelated	5 calendar days	10 calendar days
Grades 1 and 2 AND resulting in "hospitalization"		
Possibly, Probably, Definitely	10 calendar days	10 calendar days
Unlikely, Unrelated	10 calendar days	10 calendar days
After 30 days of last active treatment/therapy		
Grades 3 and 4 AND meeting the definition of "serious"		
Possibly, Probably, Definitely	10 calendar days	10 calendar days
Unlikely, Unrelated	No reporting required	No reporting required
Grades 1 and 2 AND resulting in "hospitalization"		
Possibly, Probably, Definitely	10 calendar days	10 calendar days
Unlikely, Unrelated	No reporting required	No reporting required

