### **6.1 Expected Toxicities**

#### 6.1.1 Panitumumab

**Per the package insert for systemic panitumab, the expected toxicities for panitumab are as follows, where the asterisk (\*) signifies a common event:**

*Eye disorders:* keratitis, ulcerative keratitis, growth of eyelashes.

*Gastrointestinal:* stomatitis/mucositis, intestinal obstruction, nausea, diarrhea, vomiting, dry mouth.

*General disorders and administration site conditions:* Infusion related reaction, fatigue, mucosal inflammation, dehydration, paresthesia.

*Infections:* paronychia\*, conjunctivitis, sepsis, fatal infections/complications including necrotizing fasciitis.

*Immune system disorders:* hypersensitivity reaction.

*Metabolism and nutrition disorders:* hypomagnesemia, hypocalcemia, hypokalemia.

*Skin and subcutaneous tissue disorders:* acneiform dermatitis\*, pruritus\*, erythema\*, rash\*, exfoliative rash\*, skin ulcer/abscess\*, acne, skin exfoliation\*, dry skin\*, nail disorder\*, skin fissure \*, Stevens-Johnson syndrome, toxic epidermal necrolysis, bullous mucocutaneous skin disease, photosensitivity.

*Respiratory:* Pulmonary fibrosis/interstitial lung disease, bronchospasm associated with infusion reaction, dyspnea associated with infusion reaction, cough, epistaxis.

*Renal:* acute renal failure associated from severe diarrhea and dehydration.

*Miscellaneous:* fever associated with infusion reaction, chills associated with infusion reactions hypotension associated with infusion reaction.

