## 7.3 Definitions

**Adverse event (AE)** - An adverse event is any untoward medical experience or change of an existing condition that occurs during or after treatment, whether or not it is considered to be related to the protocol intervention.

**Unexpected Adverse Event [21 CFR 312.32 (a)]** – An adverse event is unexpected if it is not listed in the investigator’s brochure and/or package insert; is not listed at the specificity or severity that has been observed; is not consistent with the risk information described in the protocol and/or consent; is not an expected natural progression of any underlying disease, disorder, condition, or predisposed risk factor of the research participant experiencing the adverse event.

**Expected Adverse Event** - Any event that does not meet the criteria for an unexpected event OR is an expected natural progression of any underlying disease, disorder, condition, or predisposed risk factor of the research participant experiencing the adverse event.

**Serious Adverse Event (SAE) [21 CFR 312.32]** - defined as any expected or unexpected adverse event that results in any of the following outcomes:

- Death
- Is life-threatening experience (places the participant at immediate risk of death from the event as it occurred)
- Unplanned hospitalization (equal to or greater than 24 hours) or prolongation of existing hospitalization
- A persistent or significant disability/incapacity

- A congenital anomaly/birth defect
- Secondary malignancy
- Any other adverse event that, based upon appropriate medical judgment, may jeopardize the participant’s health and may require medical or surgical intervention to prevent one of the outcomes listed above (examples of such events include allergic bronchospasm requiring intensive treatment in the emergency room or at home, blood dyscrasias or convulsions that do not result in inpatient hospitalization, or the development of drug dependency or drug abuse).

**Unanticipated problem (UP)** – Any incident, experience, or outcome that **meets all three** of the following criteria:

1. Unexpected (in term nature, severity, or frequency) given the following: a) the research procedures described in the protocol-related documents such as the IRB approved research protocol, informed consent document or Investigator Brochure (IB); and b) the characteristics of the participant population being studied; **AND**

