#### COH IRB Adverse Event Reporting Timelines

Required Reporting Timeframe to COH IRB		
Attribution	Unexpected	Expected
Death while on active treatment/therapy or within 30 days of the last day of active treatment/therapy		
Possibly, Probably, Definitely	5 calendar days 	Annual
Unlikely, Unrelated	Annual	Annual
Grades 3 and 4		
Possibly, Probably, Definitely	5 calendar days 	Annual
Unlikely, Unrelated	Annual	Annual
Grade 1 and 2		
Possibly, Probably, Definitely	5 calendar days 	Annual 
Unlikely, Unrelated	Annual 	Annual 

 These events must be reported in the time frame if they meet the definition of an unanticipated problem.

 For studies that are not first in human, Phase I and first in pediatric trials, only grades 3-5 must be reported at annual review.

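### Table 7.3.1 sets no expedited DSMC report for a treatment-related, expected death after day 30, while related, expected non-fatal serious events in the same window are due in 10 calendar days

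*Combined protocol and SAP*

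**What the plan says.** Section 7.4 sends serious adverse events to the DSMC and IRB under an institutional policy, which is not reproduced, and under the table that follows (Table 7.3.1).

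- **Late deaths.** The DSMC part has a block headed "Death after 30 days of last active treatment/therapy". For deaths possibly, probably or definitely related to treatment, the unexpected column gives 5 calendar days and the expected column gives "No reporting required".
- **Late non-fatal events.** The block for other events after 30 days has a row for "Grades 3 and 4 AND meeting the definition of" serious, and a row for grade 1-2 events that lead to hospitalization. For related events, both rows give "10 calendar days" in both columns.
- **Seriousness.** Section 7.3 says that a serious adverse event is "defined as any expected or unexpected adverse event that results in any of the following outcomes", and death is the first outcome listed.
- **Expectedness.** Section 7.3 also treats an event as unexpected if it is not listed at the severity observed. Section 6.1.1 lists "sepsis, fatal infections/complications including necrotizing fasciitis" among the expected panitumumab toxicities.
- **Periodic reporting.** Section 7.2 has the PMT report to the DSMC every 6 months for a Risk Level 3, phase II study, covering toxicity, response, PFS and OS.

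**The concern.** Reporting rules normally tighten as the outcome worsens. Here the requirement disappears at the worst outcome, in one column only. Section 7.3 makes death serious whether or not it was expected, and the table does not let expectedness excuse the related non-fatal late events. Nothing in the protocol explains why it should excuse the related fatal ones.

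An exemption for late deaths makes sense for deaths from the cancer itself. Those already fall in the unlikely or unrelated row, which requires no report. The cell in question is for deaths attributed to study treatment.

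What is at stake is the speed and completeness of safety oversight. Describing the safety of re-challenge is a secondary objective, and Section 7.2 makes the PMT responsible for implementing any stopping rules for safety. A late toxic death is information the DSMC would want with its attribution while the trial is still treating patients.

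**Working it through.** No sample size, power or event count enters this point. The check is a cell-by-cell reading of the table, followed by a search for other routes to the DSMC.

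**1. The cells.** DSMC part of Table 7.3.1, more than 30 days after last treatment, related events (possibly, probably or definitely):

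| Event | Unexpected | Expected |
|---|---|---|
| Grade 1-2 with hospitalization | 10 calendar days | 10 calendar days |
| Grade 3-4, serious | 10 calendar days | 10 calendar days |
| Death | 5 calendar days | none |

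For unlikely or unrelated events in this window, no row requires a report. In the unexpected column the limit shortens at death, from 10 days to 5. In the expected column it goes from 10 days to none. The inversion is confined to one of the six related cells. Every cell of the late-death block is filled in, so the reading does not depend on a table broken in extraction. The blank cells belong to the separate block for deaths on treatment or within 30 days. They may be merged cells, and nothing here rests on them.

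**2. Which deaths fall in the cell.** Under Section 7.3, a listed toxicity that turns fatal is unexpected unless it is listed at that severity. In the Section 6.1 lists:

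- Fatal infections on panitumumab are listed as fatal, so such a death is expected and falls in the empty cell.
- Interstitial lung disease (panitumumab, irinotecan), intestinal perforation and neutropenic infection (irinotecan) are listed without fatal severity. A related late death from one of these reads as unexpected and is due in 5 calendar days.

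**3. Other routes for a related, expected death after day 30.**

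- *Earlier phase of the same event.* If the toxicity was first a related, serious grade 3-4 event, that already required a report in 5 or 10 days. Study calendar note f follows serious events that start within 30 days of the last drug until they resolve or stabilize. The exposed case is an event with no earlier reportable serious phase.
- *Adverse event forms.* Note m ends collection 30 days after the last dose, with an extension only for ongoing reportable, related events.
- *Survival follow-up.* Note aa uses record review, the social security registry or a phone call. No attribution is asked for.
- *IRB table.* Its only death row is "Death while on active treatment/therapy or within 30 days of the last day of active treatment/therapy". The expected column requires annual reporting at most.
- *Unanticipated problems.* Section 7.3 requires the problem to be unexpected.
- *Supplier.* Section 7.5.1 also requires the event to be unexpected. Sections 7.5 and 7.5.3 require prompt notice of potential safety issues but set no rule for an individual death.
- *PMT report.* This does reach the DSMC, every 6 months.

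**4. Resulting delay.** A death that becomes known just after one PMT report waits up to about 6 months for the next. A related, expected non-fatal serious event in the same window is due in 10 calendar days.

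**The case against.** The case on the other side is substantial, and most of it stands.

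- A reader might infer that late drug-related deaths bypass the DSMC. The documents do not support that. The six-monthly PMT report carries toxicity and OS, and unexpected related late deaths are due in 5 calendar days. What is missing is an expedited report for one class of death.
- A reader might also infer that almost any late toxic death would count as expected, because the Section 6.1 lists are long. The severity clause in Section 7.3 rules that out. On the lists given, fatal infection on panitumumab is the clear case. The package inserts are not reproduced, so a wider class cannot be shown.
- The PMT and DSMC are not the only oversight. The IRB receives events, including grade 5 events at annual review, and the supplier receives every PMT report. Neither gives the DSMC an expedited report of this death.
- The institutional policy cited in Section 7.4 may require more than the table does. This cannot be checked here and could close the gap.
- The cell changes no endpoint or analysis, the deaths still count in OS, and the table is the institution's own for Risk Level 3 and 4 studies. That bears on the weight of the point. It does not explain the inversion, and nothing in the documents bars this trial from a stricter rule.

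**Conclusion.** The inconsistency is real and narrow. One cell leaves a related, expected death after day 30 without an expedited DSMC report, while both related, expected non-fatal rows in that window carry 10 calendar days. In practice it affects deaths from toxicities listed at fatal severity with no earlier reportable serious phase. Such a death may first reach the DSMC up to about 6 months later, possibly as an OS event without a required attribution.

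No probability can be given, because the documents supply no rate for such deaths. For scale only, one death among 25 participants is 1/25 = 4%.

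The conclusion rests on three assumptions: that the table is applied as written, that expectedness is judged on the Section 6.1 lists and the Section 7.3 definition, and that the cited institutional policy adds nothing. The change is worth making because it is cheap and concerns safety oversight. The efficacy conclusions do not depend on it.

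**What to change.** In the DSMC part of Table 7.3.1, in the block for deaths more than 30 days after last treatment, take the row for possibly, probably or definitely related and the expected column. Replace the exemption with a reporting limit no longer than the 10 calendar days that the table already sets for related, expected serious events in that window. When making the edit, check the cell against the institutional policy cited in Section 7.4 so that the two agree.

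The cost is one table cell in an amendment, at most a few extra reports, and a rule slightly stricter than the institution's standard table. The edit does not by itself extend adverse event collection beyond day 30, and it changes no endpoint or analysis.

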#### COH IRB Adverse Event Reporting Timelines

Required Reporting Timeframe to COH IRB		
Attribution	Unexpected	Expected
Death while on active treatment/therapy or within 30 days of the last day of active treatment/therapy		
Possibly, Probably, Definitely	5 calendar days 	Annual
Unlikely, Unrelated	Annual	Annual
Grades 3 and 4		
Possibly, Probably, Definitely	5 calendar days 	Annual
Unlikely, Unrelated	Annual	Annual
Grade 1 and 2		
Possibly, Probably, Definitely	5 calendar days 	Annual 
Unlikely, Unrelated	Annual 	Annual 

 These events must be reported in the time frame if they meet the definition of an unanticipated problem.

 For studies that are not first in human, Phase I and first in pediatric trials, only grades 3-5 must be reported at annual review.

## 7.5 Reporting to Amgen

The principal investigator or his designee will immediately advise Amgen of any potential safety issues, including independent or regulatory/institutional/safety monitoring committee actions or change in study conduct for safety reasons, and will consult and work with Amgen on any such potential issues. The timing of and mechanisms for notification to Amgen are detailed in the subsections that follow.

### 7.5.1 Serious Unexpected Suspected Adverse Events

**Within 10 days** of the study team learning of the event, the principal investigator or his designee will notify Amgen of any adverse events that meet **all** of the following criteria:

- Serious, (all grade 3 and 4, and all grade 1 or 2 resulting in hospitalization)
- Unexpected to panitumab per the package insert (see also Section 6. 1 of the protocol for a listing of toxicities found in the package insert)
- Suspected (possibly, probably or definitely related) to panitumab.

To notify Amgen, the principal investigator or his designee fax or securely email the completed COH iRIS Safety Report Form **and** the completed study specific SAE Fax Coversheet to Amgen to the email address or fax number on the coversheet. The communication will signify this is for Amgen ISS 20149076.

### 7.5.2 Non-SAE Unanticipated Individual Safety-Related Events

Within 10 days of the study team learning of the event, the principal investigator or his designee will notify Amgen of any non-SAE unanticipated individual safety related events, to include but not limited to the following:

- misuse/abuse,
- overdose,
- pregnancy/fetal exposure
- lactation exposure
- administration of expired study agent

To notify Amgen, the principal investigator or his designee will fax or securely email the completed COH iRIS Safety Report Form **and** the completed study specific SAE Fax Coversheet to Amgen to the email address or fax number on the coversheet. **NOTE:** In the event of a pregnancy/fetal exposure, the study team will contact the Amgen ISS program manager [name] ([[contact]](mailto:[contact])) or his designee to request a pregnancy notification worksheet which, when completed, will accompany the aforementioned documents as part of the submission packet to Amgen.

### 7.5.3 Safety Issues and Safety-Related Changes to Study Conduct

The principal investigator or his designee will immediately advise Amgen of any potential safety issues, including independent or regulatory/institutional/safety monitoring committee actions or change in study conduct for safety reasons (e.g. hold to accrual for safety), and will consult and work with Amgen on any such potential issues.

Safety related changes to study conduct, protocol amendments, etc. will be emailed to the Amgen ISS program manager [name] ([[contact]](mailto:[contact])).

### 7.5.4 Protocol Management Team (PMT) Data Safety Monitoring Reports

The principal investigator or his designee will provide all Protocol Management Reports that are submitted to the COH DSMC to Amgen within (+/-) 10 days of their submission to the DSMC. These reports

will be generated and submitted to the DSMC and Amgen at least bi-annually and will therefore substitute for the annual aggregate safety report to Amgen.

PMT/DSM Reports will be emailed to the Amgen ISS program manager [name] ([contact]).

## **8.0 AGENT INFORMATION**

---

*The NCCN guidelines include the use of panitumumab with FOLFIRI (irinotecan, 5-FU, leucovorin) in the first line treatment or in the second line treatment for colorectal cancer (extended RAS wild-type). FOLFIRI consists of the combination of FOLinic acid, Fluorouracil, and IRInotecan. FOLFIRI is commonly used in the first, second, and third line treatment of metastatic colorectal cancer in combination with cetuximab or panitumumab.*

### **8.1 Panitumumab**

A complete description, toxicity, and pharmacology of panitumumab is detailed in the package insert accessible at [www.vectibix.com](http://www.vectibix.com)

Panitumumab will be manufactured and packaged by Amgen and distributed using Amgen's clinical investigational product distribution procedures. Panitumumab must be prepared and administered by a qualified and, where applicable, licensed healthcare professional.

#### **8.1.1 Other names:**

Vectibix®

#### **8.1.2 Description and molecular weight**

Panitumumab is a recombinant, human IgG2 kappa monoclonal antibody that binds specifically to the human epidermal growth factor receptor (EGFR). Panitumumab has an approximate molecular weight of 147 kDa. Panitumumab is produced in genetically engineered mammalian (Chinese hamster ovary) cells.

#### **8.1.3 Mechanism of action**

The EGFR is a transmembrane glycoprotein that is a member of a subfamily of type I receptor tyrosine kinases, including EGFR, HER2, HER3, and HER4. EGFR is constitutively expressed in normal epithelial tissues, including the skin and hair follicle. EGFR is over expressed in certain human cancers, including colon and rectum cancers. Interaction of EGFR with its normal ligands (eg, EGF, transforming growth factor-alpha) leads to phosphorylation and activation of a series of intracellular proteins, which in turn regulate transcription of genes involved with cellular growth and survival, motility, and proliferation. Signal transduction through the EGFR results in activation of the wild-type *KRAS* protein. However, in cells with activating *KRAS* somatic mutations, the *KRAS*-mutant protein is continuously active and appears independent of EGFR regulation. Panitumumab binds specifically to EGFR on both normal and tumor cells, and competitively inhibits the binding of ligands for EGFR. Nonclinical studies show that binding of panitumumab to the EGFR prevents ligand-induced receptor autophosphorylation and activation of receptor-associated kinases, resulting in inhibition of cell growth, induction of apoptosis, decreased proinflammatory cytokine and vascular growth factor production, and internalization of the EGFR. In vitro assays and in vivo animal studies demonstrate that panitumumab inhibits the growth and survival of selected human tumor cell lines expressing EGFR.

#### 8.1.4 Pharmacokinetics

Following the recommended dose regimen (6 mg/kg given once every 2 weeks as a 1-hour infusion), panitumumab concentrations reached steady-state levels by the third infusion with mean ( $\pm$  SD) peak and trough concentrations of  $213 \pm 59$  and  $39 \pm 14$  mcg/mL, respectively. The mean ( $\pm$  SD) AUC0-tau and CL were  $1306 \pm 374$  mcg•day/mL and  $4.9 \pm 1.4$  mL/kg/day, respectively. The elimination half-life was approximately 7.5 days (range: 3.6 to 10.9 days).

#### 8.1.5 Human Toxicity

See section 6.1.1.

#### 8.1.6 Formulation

Panitumumab is supplied as commercially labeled single-use 5mL vial containing 100 mg (20mg/ml) of panitumumab, 29 mg sodium chloride, 34 mg sodium acetate, and Water for Injection, USP. It is preservative free, sterile, and at pH 5.6 to 6.0.

The solution is a colorless and may contain a small amount of visible translucent-to-white, amorphous, proteinaceous, panitumumab particulates.

